Following consent and screening, participants were randomly assigned to receive Scrambler treatment versus sham at a 1:1 ratio for 10 consecutive weekdays. Recruitment was batched using a randomized block design stratifying across medication class (anti-epileptic, antidepressant, opioid or none) and pain level at screening (moderate 4-6, or severe 7-10) to promote similar distributions across groups in this small study. The rationale was to increase homogeneity between groups due to limited data that suggest response to Scrambler therapy may differ due to interference of medications used for pain.²³ Randomization assignments were assigned by a third-party utilizing www.randomizer.org.

Scrambler therapy was administered via the GEOMC Pain Scrambler, model MC-5A. Electrodes were placed on participants receiving treatment within the dermatome above and below the level of injury, in a sufficiently sensitive area closest to the pain. For instance, if the patient had pain in the back from C3 to C8, a set of electrodes would be placed at C2 (above the pain) and T1 (below the pain.) Stimulation intensity was increased until a maximum tolerable threshold

was reached without being painful, per the established protocol. If the patient felt a constant burn, sting or feeling of discomfort, electrodes were repositioned. The exact electrode positioning depended on the demarcation of the surface pain area, and analgesic response of the patient. Once the channel was regulated to the patient's maximum intensity, pain was assessed by asking the patient how s/he felt in the area of pain covered by the electrodes and adjusted for desired effect of reduced pain and/or analgesic response. Additional channel-pairs were similarly implemented as necessary based on size of pain area, up to 5 pairs in total. Electrodes remained in the established position and intensity for 35 minutes from the time of proper placement was instituted. As central pain is often more pervasive as compared with peripheral neuropathy, more than one area was often targeted.

For the sham group, small motors (<1 cm) which produce a vibratory sensation similar to a wearable activity tracker (i.e., FitBit) were connected to each electrode to simulate Scrambler stimulation but without electrical charge. Channel-pairs were similarly applied in a sufficiently sensitive dermatome closest to the pain, surrounding the level of spinal cord injury. The sham sensation was applied for 35 minutes.

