For both groups, the Scrambler machine was kept behind a curtain to help preserve masking. The machine itself was turned on for all participants, though without emitting any stimulation in those receiving sham, so that the alert indicating termination of treatment would be heard by all participants regardless of treatment assignment. Because treatment effect has been shown to vary across technicians, one technician was trained in the proper delivery of Scrambler treatment and performed all interventions.

Study objectives and measures:

Our primary objective was to test the hypothesis that Scrambler therapy is an effective, acceptable, feasible and safe treatment of persistent central neuropathic pain for patients with NMOSD. To test this hypothesis, we performed a randomized single blind, sham-controlled trial testing Scrambler therapy in patients with NMOSD. The primary outcome was feasibility and acceptability. Secondary endpoints included both safety and effectiveness at the end of the 10-day treatment period. Feasibility of treatment was examined to determine whether the intervention was appropriate for this patient population, toward the effort of informing a larger, Phase III study. This was measured by assessing the following: 1) adherence to visit schedule and 2) response to the following question asked directly after completion of the 10-day treatment period: "Do you think you received treatment?" (Yes/No). Acceptability was measured by assessing response to the following question, also asked directly following the treatment course: "Would you want to continue treatment in clinic, if available?" (Yes/No).

Safety of the intervention was evaluated by comparing Adverse Events (AEs) and Serious Adverse Events (SAEs) in the treated versus sham groups. These were monitored and documented prior to initiation of each treatment daily, at termination of final treatment, and at 30- and 60-day follow-up.

Effectiveness was evaluated based on degree of improvement in pain, comparing the treatment group to sham. Prior to initiation of Scrambler therapy and at completion of treatment, patients were asked to rate their pain by the 11-point NRS score. Patients additionally reported NRS pain

scores at 30- and 60- days following therapy completion to assess sustainability of treatment effect.

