Although not powered appropriately, an exploratory objective aimed to assess the relationship between improved pain and other co-occurring symptoms. Prior to initiation of Scrambler therapy, patients were asked to complete each of the following measurement tools to determine baseline pain severity and interference, anxiety, depression, and sleep disturbance, respectively: Brief Pain Inventory (BPI), Neuro-QoL [Quality of Life in Neurological Disorders] Short Form v1.0 - Anxiety, Neuro-QoL Short Form v1.0 - Depression, and Neuro-QoL Short Form v1.0 - Sleep Disturbance. Measurement tools were accessed by participants via a secure online portal. Participants were provided with an alphanumeric code that enabled their responses to be linked to their demographic and clinical data in a confidential manner. Questionnaires were mailed to participants without internet access with a postage-paid envelope provided for return of questionnaires. Patients again completed all measurement tools at end of treatment, and at 30- and 60-days following end of treatment.

Statistical analysis:

As one measure of feasibility of treatment, adherence to visit schedule was ascertained. We report the number of patients in each group who were able to complete all treatments. Fisher's exact test was performed to assess if adherence is independent of group assignment. For each of the two survey questions used to assess feasibility and acceptability, as described above, a 95% confidence interval for the proportion of participants answering "Yes" was calculated.

Given the small number of patients in the study, exact binomial confidence intervals were calculated since normal distribution could not be assumed.

Descriptive statistics were used to report AEs and SAEs. Incidence and severity were compared between groups.

Effectiveness was based on degree of improvement of pain and compared NRS pain scores in the treatment group and sham group using the Friedman One-Way Repeated Measure Analysis of Variance by Ranks test at baseline, following treatment, and at 30- and 60-day follow-up.

Wilcoxon signed-rank testing was used to determine sustainability over time by comparing scores at baseline to those following treatment, at 30-day follow-up and at 60-day follow-up. A chi-squared analysis comparing the number of treated patients who thought they received treatment versus the number of sham patients who thought they received treatment was performed to determine if masking was effective.

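### The chi-squared test of treatment guesses at 11 per arm is the only analysis tied to the masking conclusion, and a non-significant result cannot show that masking worked

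*Combined protocol and SAP*

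**What the plan says.** The masking check is one sentence in the Statistical analysis section. It opens with the active arm: "A chi-squared analysis comparing the number of treated patients who thought they received treatment". It then brings in the sham arm and gives the purpose: "versus the number of sham patients who thought they received treatment was performed to determine if masking was effective". It names the test and its purpose. It gives no significance level, continuity correction, margin, blinding index or rule for reading the result.

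The data come from a Yes/No question on whether the patient thinks treatment was received. Study objectives and measures lists it under feasibility, as a "response to the following question asked directly after completion of the 10-day treatment period".

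The Statistical analysis section also plans, for each of the two survey questions, "a 95% confidence interval for the proportion of participants answering" Yes, by the exact binomial method. The guess question is one of the two, so an estimate and an interval are planned for it. They serve feasibility and acceptability, no arm is stated, and they are not linked to the masking decision.

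On design: "we performed a randomized single blind, sham-controlled trial testing Scrambler therapy in patients with NMOSD".

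**The concern.** A test of no difference can give evidence that guesses differ between arms. With 11 patients per arm, failing to find a difference is weak evidence that there is none. Because the test is the only analysis tied to the masking question, a statement that masking was effective would have to rest on a non-significant p-value.

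Three features of the trial make this matter:

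- Patients are the blinded party, and effectiveness rests on their own rating: "patients were asked to rate their pain by the 11-point NRS score".
- Randomization and Masking describes different sensations in the two arms. For active treatment, "Stimulation intensity was increased until a maximum tolerable threshold" was reached. The sham used small motors without electrical charge, "which produce a vibratory sensation similar to a wearable activity tracker". Partial unmasking is therefore possible.
- The guess question is part of the primary feasibility outcome, which is meant to inform a Phase III study. An unsupported masking claim could be carried into the planning of that study.

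**Working it through.** **Plan's own figures.** The documents give no power, margin or detectable difference for the masking test. The one sample-size figure concerns pain: 11 per arm, change 2.5, SD 2, 80% power. Read as a two-arm comparison at two-sided 0.05, it reproduces: n = 2(1.960 + 0.842)² × 2² / 2.5² = 10.05, so 11 per arm. A two-sample t-test at 11 per arm has 79.6% power. That calculation says nothing about guesses.

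**Inputs.** From the documents: 11 per arm, a Yes/No answer, a chi-squared test. Assumed: two-sided alpha 0.05, all 22 patients answer, and the true Yes rates shown below.

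**Test statistic.** With a and b Yes answers out of 11 in the two arms:

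- uncorrected: X² = 22(a − b)² / [(a + b)(22 − a − b)]
- continuity-corrected: replace (a − b)² by (|a − b| − 1)²

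**Power.** Sum Bin(a; 11, p₁) × Bin(b; 11, p₂) over the 12 × 12 possible outcomes with p ≤ 0.05.

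| True Yes rates | Gap (points) | Power, uncorrected | Power, corrected |
|---|---|---|---|
| 90% v 60% | 30 | 34% | 19% |
| 80% v 50% | 30 | 30% | 17% |
| 90% v 50% | 40 | 54% | 36% |
| 90% v 30% | 60 | 88% | 76% |
| 90% v 20% | 70 | 97% | 91% |

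Fisher's exact test gives the same power as the corrected test at these rates. A 30-point gap is missed about two times in three without correction, and more than four times in five with it.

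**What a non-significant result leaves open.** The Newcombe 95% interval for d = p₁ − p₂ combines the Wilson limits (l, u) of each arm:

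- lower = d − √[(p₁ − l₁)² + (u₂ − p₂)²]
- upper = d + √[(u₁ − p₁)² + (p₂ − l₂)²]

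*10/11 v 6/11.* X² = 22 × 16 / (16 × 6) = 3.67, p = 0.056 (0.151 corrected). The Wilson limits are 0.623 to 0.984 and 0.280 to 0.787, and d = 0.364.

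- lower = 0.364 − √(0.286² + 0.242²) = −0.011
- upper = 0.364 + √(0.075² + 0.265²) = 0.639

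So a 36-point observed gap is non-significant, with an interval of −1 to +64 points.

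*8/11 v 8/11.* X² = 0, p = 1.0. The Wilson limits are 0.434 to 0.903 in each arm, and the half-width is √(0.293² + 0.175²) = 0.341. Identical guesses still give −34 to +34 points.

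*All tables.* Among tables with a defined statistic and p ≥ 0.05, the smallest value of the further limit is 29.6 points, at 10/11 v 10/11 (and its mirror, 1/11 v 1/11). This concerns the limit further from zero, not the width: 11/11 v 10/11 has a narrower interval (−18 to +38, 56 points wide, against 59), but its further limit is 38. If all 22 patients answer Yes, chi-squared is undefined and the interval is −26 to +26.

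**Whether the planned exact interval fills the gap.** It describes one proportion. If it were taken over all 22 patients, 14/22 would give 41% to 83% whether the arms were 7/11 and 7/11 or 11/11 and 3/11. If it were taken by arm, two separate intervals would still not be an interval for the difference.

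**The case against.** The strongest reply is that the plan commits no stated error. It names a test and a purpose and is silent on interpretation. This stands: a reader might infer that the sponsor will treat p > 0.05 as proof of masking, but no sentence says so. What remains is that the plan supplies nothing else from which a positive conclusion could be drawn.

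A reader might also infer that no estimate or interval is planned for the guess question. That is not so: the exact binomial interval covers it. What is missing is an interval for the between-arm difference, or another criterion, tied to masking.

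Nor is the test uninformative. It detects gaps of 60 to 70 points in 88% to 97% of trials (76% to 91% with correction). The power figures for smaller gaps depend on assumed Yes rates.

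Nor do the documents show that masking failed. The motors were meant to imitate the stimulation, the machine stood behind a curtain, and it was switched on for everyone so that all heard the end alert. These measures lower the chance of unmasking, but they are procedures and do not assess whether masking held.

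The sample-size paragraph mentions a 60% difference in proportions. A reader might take this as the design value for the masking test. It has no base rate and is not described as belonging to that test, so it is not used here.

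Finally, the test already requires counts by arm, so the remedy is mostly reporting. That is true. It keeps the cost low but does not remove the problem of inference.

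**Conclusion.** The concern holds in a limited form. The chi-squared test is the only analysis tied to deciding whether masking was effective. At 11 per arm it can reveal gross unmasking but cannot support a positive masking conclusion. Power for a 30-point gap in belief is 30% to 34% (17% to 19% with continuity correction), and every non-significant table with a defined statistic leaves a gap of about 30 points or more unexcluded in at least one direction. The power figures rest on two-sided alpha 0.05, complete answers and illustrative Yes rates. The intervals depend only on the counts and the 95% level. The sponsor should act on this, but it changes no pain or safety analysis.

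**What to change.** Beside the planned chi-squared test, report for the guess question the Yes proportion in each arm and the between-arm difference with a 95% confidence interval, for example Newcombe. Describe the test as looking for evidence of unmasking. State that a non-significant result will not be taken to show that masking was effective.

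The cost is one interval from counts already collected, plus wording. Sample size is not part of the fix: 22 patients were enrolled, and 80% power for a 30-point gap would need 32 to 43 per arm (uncorrected test). The downside is that the interval will be wide, with its further limit about 30 points or more from zero for any non-significant table with a defined statistic. The report may therefore have to say that masking could not be confirmed.

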The target sample size of 22 (11 per arm) was based on previous studies which suggest that the average pain value at baseline is at least 4 on the 0-10 NRS with a standard deviation of the original pain value expected to fall in the range of 1-1.5 in this patient population. A conservative estimate of the standard deviation of the change across patients from Day 1 to Day 10 was approximately up to 2. With 11 patients in each arm and under these assumptions, we were able to detect a change of 2.5 points in the Scrambler group at 80% power, with a difference in proportions of 60% between the two groups.

To explore the impact on co-occurring symptoms when intervening on pain, scores were tabulated for each of the following based on measurement tool data: anxiety, depression, sleep

disturbance and pain interference. Friedman One-Way Repeated Measure Analysis of Variance by Ranks was tabulated for each symptom, comparing the change at baseline, following treatment, and at 30- and 60-day follow-up timepoints in each arm. A subanalysis was similarly conducted in those patients who “responded” to Scrambler treatment versus sham. Based on a cohort of adult patients with spinal cord injury who reported clinically meaningful change in pain over time, “response” was defined as patients with a decrease in NRS pain scores of 1.80 points between baseline and end of treatment.

Demographic and clinical characteristics were compared between Scrambler and sham groups using Mann-Whitney *U* and Chi-squared testing, as appropriate.

Data availability:

Public Law 110-85 (also known as the FDA Amendments Act of 2007) mandates registration and results reporting of "applicable clinical trials" in ClinicalTrials.gov. We support efforts to promote data sharing toward the advancement of science and registered this clinical trial, providing trial design, eligibility criteria and outcomes measures.

Classification of evidence:

This study provides Class II evidence of Scrambler therapy use in patients diagnosed with NMOSD who have central neuropathic pain.

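### The 80% power is worded as a change within the Scrambler arm but best fits a Scrambler-minus-sham difference, and the plan names no between-arm test of pain to carry it

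*Combined protocol and SAP*

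**What the plan says.** All references are to the combined protocol and SAP.

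- **Statistical analysis, sample-size paragraph.** With 11 patients in each arm, "we were able to detect a change of 2.5 points in the Scrambler group at 80% power, with a difference in proportions of 60"% (Scrambler against sham). The spread behind this is given as follows: "A conservative estimate of the standard deviation of the change across patients from Day 1 to Day 10 was approximately up to 2". No alpha, sidedness or test is stated, and the 60% has no endpoint, arm rates or test.
- **Study objectives and measures.** "Effectiveness was evaluated based on degree of improvement in pain, comparing the treatment group to sham". Its place in the hierarchy is also given: "Secondary endpoints included both safety and effectiveness at the end of the 10-day treatment period". Feasibility and acceptability are primary.
- **Statistical analysis, effectiveness.** The analysis "compared NRS pain scores in the treatment group and sham group using the Friedman One-Way Repeated Measure Analysis of Variance by Ranks test" over the four time points. In addition, "Wilcoxon signed-rank testing was used to determine sustainability over time by comparing scores at baseline to those following treatment" and at the two follow-ups.
- **Statistical analysis, last paragraph.** The plan's one two-sample rank test is assigned elsewhere: "Demographic and clinical characteristics were compared between Scrambler and sham groups using Mann-Whitney" U and chi-squared tests.

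**The concern.** A power statement needs a contrast, a test and an alpha. Here only a contrast is given, a change within the Scrambler arm, and at the usual 5% level it does not produce the stated 80%. The same inputs do produce 80% for a different contrast, the difference from sham. That difference is what the plan calls effectiveness, but the tests named for pain do not examine it.

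This is the plan's only power statement. Taken literally, it promises 80% power whenever treated patients improve by 2.5 points. A reader could then over-read a non-significant comparison with sham as evidence of no effect. A reader could also take two separate within-arm results, one significant and one not, for the powered comparison of the arms.

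**Working it through.** **Inputs.** n = 11 per arm, SD of change σ = 2 (the stated upper end), effect 2.5 points and power 80% all come from the sample-size paragraph. Alpha is not stated there. I assume two-sided 0.05; the only hint is the 95% confidence level used for the survey questions.

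**1. Reproducing the 80% as a between-arm difference (two-sample t).**
- Standard error = σ√(2/n) = 2 × √(2/11) = 0.853.
- Noncentrality = 2.5 / 0.853 = 2.93, with 20 df and critical value 2.086.
- Power = **79.6%**. The difference detectable with 80% power is 2.51 points.
- The normal approximation gives 83.4%, and a required n of 11 per arm.
- Mann-Whitney U on the change scores, by simulation with normal data: about 76%.

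**2. The contrast as worded, a change within the Scrambler arm (one-sample t on change).**
- Standard error = σ/√n = 2/√11 = 0.603.
- Noncentrality = 2.5 / 0.603 = 4.15, with 10 df and critical value 2.228.
- Power = **96.1%**. The change detectable with 80% power is 1.88 points, and 8 patients would be enough for 2.5 (85.6%; 7 give 78.6%).
- Wilcoxon signed-rank by simulation: about 94% to 95%.

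**3. Other routes to roughly 80%.**
- One-sample t within the arm at two-sided alpha 0.0095: 80%.
- Exact signed-rank within the arm at 0.05/3, for three comparisons with baseline: about 83%. At 0.0125: about 78%.
- Friedman within one arm at 5%, four time points, independent errors, SD of change 2: about 94% if the 2.5-point drop is fully sustained or present only at end of treatment, but about 81% if it half fades by both follow-ups.
- Fisher's exact test for a 60-point difference, 11 per arm: 80.0% at 5% vs 65% or 35% vs 95%. Over the possible rates it runs from 73.4% (20% vs 80%) to 90.1% (0% vs 60%, or 40% vs 100%).

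**4. If 2.5 is the raw Scrambler change but the test is against sham.** The net difference is 2.5 minus the sham improvement. The documents give no sham change, so the values 0, 0.5 and 1.0 are assumptions. Two-sample t, two-sided 5%:

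| SD of change | Sham 0 (net 2.5) | Sham 0.5 (net 2.0) | Sham 1.0 (net 1.5) | Detectable at 80% |
|---|---|---|---|---|
| 2 | 80% | 61% | 39% | 2.51 |
| 1.75 | 89% | 72% | 48% | 2.20 |
| 1.5 | 96% | 84% | 61% | 1.88 |

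Power of 80% survives a sham improvement of 0.5 if the SD is about 1.59 or less, and of 1.0 if it is about 1.19 or less.

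**5. Contrast against named test.** Friedman ranks each patient's own scores over time and has no term for two independent arms. The signed-rank test compares each later score with that patient's baseline. Neither tests the Scrambler-minus-sham difference that the objectives section calls effectiveness. Mann-Whitney could, but it is assigned to demographic and clinical characteristics.

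**The case against.** The strongest reply is that nothing has been miscalculated. The figures reproduce, the sentence refers to both arms and to a difference between the groups, and a fair reader might take 2.5 as net of sham. On that reading 80% stands and sham improvement does not erode it. All of this is right. It leaves a contrast that is mislabelled at the usual alpha, with no pain test attached to it.

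A second reply is that the between-arm match is not unique. This also stands. Step 3 shows within-arm and proportion-based routes to about 80%. The plan states no multiplicity adjustment, fading pattern or response rates, so none of these can be confirmed; with no alpha given, none can be excluded. The 60% may even be part of the original basis, since the plan defines a responder (a 1.80-point decrease). It should not be deleted without asking the sponsor.

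A third reply is that the effectiveness paragraph words Friedman as a comparison of the two groups. That shows the intention, but the method does not deliver it, and the plan itself describes Friedman for the co-occurring symptoms as run in each arm.

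Two stronger readings are tempting and are not supported. One is that 80% cannot be the power of any named test at 5%: Friedman within one arm reaches about 81% under a half-fading effect. The other is that the trial has only 39% to 61% power: this needs 2.5 to be a raw change, the SD to be at its ceiling, and sham values that the documents do not give.

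**Conclusion.** The point holds as a minor one. At an assumed two-sided 5% level and SD 2, the stated 80% matches a Scrambler-minus-sham difference (79.6%) and not the within-Scrambler change in the sentence (96.1%). This is the best-fitting reading, not a proven one, because alpha, sidedness and test are absent. Whichever reading was meant, the tests named for NRS pain do not compare the arms, so the plan contains no pain test with 80% power for Scrambler versus sham. Erosion to 61% or 39% is conditional on 2.5 being a raw change, on the assumed sham improvements of 0.5 or 1.0 points, and on SD 2; a smaller SD softens it.

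A reader might infer that the sample size is wrong. It is not: 11 per arm is what the between-arm calculation gives. The consequence is confined to how the pain result is read, since effectiveness is secondary and the primary outcome is feasibility and acceptability.

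**What to change.** 1. Name a between-arm test of Day 1 to Day 10 NRS change as the effectiveness comparison, for example Mann-Whitney U on change scores. Keep Friedman and signed-rank as within-arm descriptions, and say that the stated power does not apply to them. The document is written in the past tense, so if the test is added after the pain scores by arm were seen, label it as such.
2. Restate the power along these lines: *With 11 per arm, an SD of change of 2 and two-sided alpha 0.05 [sponsor to confirm], there is about 80% power by two-sample t-test (about 76% by Mann-Whitney) for a Scrambler-minus-sham difference of 2.5 points.*
3. Give the endpoint, arm rates and test behind the 60% difference in proportions, or drop it if it has no basis.

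The cost is a few reworded sentences and one extra analysis of data already collected. The sample size does not change. The downside is a slightly less favourable stated capability.

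### The plan defines a clinically anchored pain responder but never compares responders with sham, and its sizing quotes a 60% difference in proportions with no event, rates or test

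*Combined protocol and SAP*

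**What the plan says.** Under Study objectives and measures, effectiveness is a secondary endpoint: "Effectiveness was evaluated based on degree of improvement in pain, comparing the treatment group to sham". Under Statistical analysis, the pain scores are to be analysed with a one-way Friedman test over baseline, end of treatment and the 30- and 60-day follow-ups. Wilcoxon signed-rank tests of each later time point against baseline are added.

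The sizing paragraph in the same section states: "The target sample size of 22 (11 per arm) was based on previous studies". It assumes the following: "A conservative estimate of the standard deviation of the change across patients from Day 1 to Day 10 was approximately up to 2". It concludes: "we were able to detect a change of 2.5 points in the Scrambler group at 80% power", and adds "with a difference in proportions of 60% between the two groups". It does not say which proportion is meant, what the rate is in either arm, or which test applies.

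The next paragraph introduces response, "defined as patients with a decrease in NRS pain scores of 1.80 points between baseline and end of treatment", and bases the threshold on clinically meaningful change in a spinal cord injury cohort. Its only stated use is to repeat the symptom analyses (anxiety, depression, sleep disturbance, pain interference) among patients who responded.

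For outcomes, the named between-arm tests of a proportion are Fisher's exact test for adherence and a chi-squared test for belief about having been treated. Chi-squared is otherwise named only for baseline characteristics.

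**The concern.** The plan has one pain criterion with a stated clinical meaning, and no result compares it with sham. Response is used after randomisation to pick a subgroup, while the randomised comparison of response itself is left out.

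This matters more because the named pain tests do not supply that comparison either. A one-way Friedman test has time as its only factor, and a signed-rank test compares paired scores within patients. Run as named, they show whether scores move over time, not whether they move more with Scrambler than with sham. A 2x2 table of responders by arm would give a valid randomised contrast from scores already collected. It would also give responder rates for planning the larger study that the trial is meant to inform.

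Separately, a reader cannot tell what the 60% in the sizing sentence refers to, and so cannot check it.

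**Working it through.** **Inputs.** From the sizing paragraph: 11 per arm, SD of change 2 (the upper value), change of 2.5 points, 80% power, 60% difference in proportions. From the paragraph after it: response at 1.80 points. Not stated, so assumed here: two-sided 5% level; 2.5 points read as the difference between arms; normal changes with equal SD; sham mean improvement of 0 to 1 point.

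**1. The plan's own figure for means.** The standard error is 2 × √(2/11) = 0.853, and 2.5/0.853 = 2.93. Normal approximation: Φ(2.93 − 1.96) = 83.4%. Two-sample t-test (20 degrees of freedom): 79.6%. The 80% for 2.5 points is reproduced.

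**2. Does 60% follow from 2.5 points and SD 2?** For cut-off c and sham mean improvement m, the responder rates are Φ((m + 2.5 − c)/2) for Scrambler and Φ((m − c)/2) for sham. Their difference is largest when c lies midway between the two means, where it equals 2Φ(2.5/(2 × 2)) − 1 = 2Φ(0.625) − 1 = 46.8 points. No cut-off gives 60. To reach 60 points, Φ(2.5/(2 × SD)) must be 0.80, so SD = 2.5/(2 × 0.8416) = 1.49, well below the 2 used for the sizing.

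**3. Power of the missing comparison.** At the 1.80 cut-off with 11 per arm (exact power, two-sided 5%):

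| Sham mean improvement | Scrambler responders | Sham responders | Difference (points) | Fisher power |
|---|---|---|---|---|
| 0 | 63.7% | 18.4% | 45.3 | 42.5% |
| 0.5 | 72.6% | 25.8% | 46.8 | 45.0% |
| 1 | 80.2% | 34.5% | 45.8 | 43.3% |

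With the normal cut-off at 2.0 in place of 1.80, Fisher power is 40.6% to 44.5%. The overall range is about 41-45%.

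As an illustration, 7 of 11 against 2 of 11 is close to the first row. Given 9 responders among 22, the two-sided Fisher p is 2 × (330 × 55 + 165 × 11 + 55 × 1)/497,420 = 40,040/497,420 = 0.08.

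**4. Power if the true difference were 60 points.** For sham rates from 0% to 40%, exact power is 73-90% by Fisher (lowest at 20% vs 80%; 80.0% at 5% vs 65% and at 35% vs 95%). By the uncorrected chi-squared test it is 87-97%. The answer depends on a test and a base rate that the plan does not give.

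**The case against.** The strongest reply is that leaving out a responder endpoint is defensible. The plan frames effectiveness as degree of improvement, a scale measure, and it is secondary in a 22-patient feasibility trial. Dichotomising is costly: about 80% power for a two-sample comparison of means falls to about 41-45% for responders. This stands as a reason not to replace the score analysis. It does not remove the gap, because the score tests named in the plan are not two-sample comparisons. The symptom subanalysis does require responders to be identified, so the counts would exist, but nothing says they will be reported or compared by arm.

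Three stronger readings are tempting, and the documents support none of them.

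- A reader might infer that the 60% is the responder difference and belongs to no planned result. The plan never names the event. It could be adherence or belief about treatment, both of which have a planned between-arm test. Step 2 in fact counts against the responder reading.
- A reader might infer that the stated power is wrong because Fisher's test gives 73-76% for sham rates of 10-30%. No test is attached to the 60%, the plan uses both Fisher and chi-squared elsewhere, and uncorrected chi-squared stays above 80% throughout.
- A reader might infer that a 1.80-point threshold misclassifies patients if the NRS is recorded in whole points. It does not: 1.80 and at least 2 then sort patients identically. Only the words for at least are missing.

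**Conclusion.** The concern holds as a gap in a secondary analysis and an unexplained sizing figure, not as an error in the sample size. The calculation for means reproduces (79.6% by two-sample t). No comparison of responders with sham is planned, and the named pain tests work within patients. This follows from the text and needs no assumption about the 60%.

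If the 60% means responders, it exceeds by about 13 points (60 − 46.8) the most that a 2.5-point difference with SD 2 can produce. That rests on normal changes with equal SDs and on reading 2.5 as the between-arm difference. If sham patients also improve and 2.5 is the change in the Scrambler arm alone, the gap widens; if the SD is near 1.5, it closes. A responder comparison at 11 per arm would have about 41-45% power by Fisher's test, so it can estimate a difference but should not be relied on to test one. The primary feasibility and acceptability outcomes are not affected.

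**What to change.** 1. Add a supportive secondary effectiveness measure: the number of responders by arm at end of treatment, defined as an NRS decrease of at least 1.80 (at least 2 if scores are whole points), among all randomised patients, with a missing end-of-treatment score counted as non-response. Compare arms by Fisher's exact test and report the risk difference with an exact 95% confidence interval. Present it alongside the score analysis, not in place of it.
2. State the event, the rate in each arm and the test behind the 60%, or delete the figure.
3. State that under the 2.5-point and SD 2 assumptions (two-sided 5%, normal changes, sham mean improvement 0 to 1) the responder comparison has about 41-45% power and is for estimation. Do not quote 73-76%, which presumes a 60-point responder difference that those assumptions do not produce.

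The cost is some wording and one more table from scores already collected. The downside is an additional secondary comparison with low power, whose non-significance must not be read as absence of effect. If it is added after results by arm are known, it should be labelled post hoc.
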